Appendix 2: Uterine Fibroid Daily Bleeding Diary (UF-DBD)

Subjects will be asked to rate any vaginal bleeding in the past 24 hours on a daily basis in the eDiary. The respective question was: "Rate the severity of any vaginal bleeding in the past 24 hours". The following answers could be selected in the eDiary by the subjects:

No vaginal bleeding
Spotting
Mild
Moderate
Severe
Very severe

Appendix 3: Uterine Fibroid Daily Symptoms Diary (UF-DSD)

Item	Response scoring
1. Rate the severity of any swelling in your abdomen or pelvic area in the past 24 hours	5 point Likert scale
2. Rate the severity of any bloating in your abdomen or pelvic area in the past 24 hours	5 point Likert scale
3. How severe was the pain in your abdomen or pelvic area, at its WORST, in the past 24 hours?	10 point scale
4. How severe was the pain in your lower back, at its WORST, in the past 24 hours?	10 point scale
5. Have you taken any pain medication in the past 24 hours?	No Yes, over the counter Yes, prescription Yes, both

Table 9-2: Uterine Fibroid Daily Symptoms Diary questionnaire

Categories Item 1:

- No swelling
- Mild
- Moderate
- Severe
- Very severe

Categories Item 2:

- No bloating
- Mild
- Moderate
- Severe
- Very severe

Appendix 4: Uterine Fibroid Symptom and Quality of Life questionnaire (UFS-QoL)

To calculate a symptom score for the *symptom severity*, a summed score based on items 1-8 is created. This will provide symptom scores with higher score values indicative of greater symptom severity or bother, and lower scores are indicative of lesser symptom severity.

Based on the lowest possible score that can be obtained and the range of raw scores, an observed sum score for the symptom severity can be projected into a percentage according to the transformation:

Transformed symptom severity score =
$$\left[\frac{(Actual raw score - Lowest possible raw score)}{Possible raw score range} \times 100\%\right]$$

with transformed scores taking values in the range 0% to 100%.

The lowest possible raw score for symptom severity as well as the score range is provided in Table 9–3.

Scale	Sum item values	Lowest and highest possible raw scores	Possible raw score range
Symptom severity	Sum scores of items 1- 8	8, 40	32

Table 9–3: Description of the UFS-QoL scoring system for assessing symptom severity.

Similar to the symptom severity, raw and transformed scores for the *Health-Related Quality of Life (HRQoL) subscales* can be derived. The HRQoL subscales comprise the 6 domains: concern, activities, energy/mood, control, self-conscious, and sexual function. The sum score for the HRQoL subscales can be derived based on the items 9-37 (see Table 9–4). Based on

Page: 56 of 58

the highest possible score and the raw score range, these raw sum scores can be transformed to a percentage according to the transformation:

 $Transformed \ HRQoL \ score = \left[\frac{(Highest \ possible \ score \ - Actual \ raw \ score \)}{Possible \ raw \ score \ range} \times 100\%\right].$

The respective highest possible raw scores and the range for each subscale is provided in Table 9–4.

Note that the scale is inverted when transforming raw HRQoL scores, such that lower *raw* HRQoL scores indicate a better HRQoL, while lower *transformed* HRQoL scores indicate a worse HRQoL.

Scale	Sum item values	Lowest and highest possible raw scores	Possible raw score range
Concern	19+115+122+128+132	5, 25	20
Activities	110+111+113+119+120+127+129	7, 35	28
Energy/mood	112+117+123+124+125+131+135	7, 35	28
Control	114+116+126+130+134	5, 25	20
Self-conscious	118+121+133	3, 15	12
Sexual function	136+137	2, 10	8
HRQoL total score	Sum of 6 subscale scores	29,145	116
Revised activities	111+113+119+120+127	5, 25	20
Revised HRQoL total score	Sum of 6 subscale scores (replacing activities with revised activities)	27, 135	108

Table 9-4: Description of the UFS-QoL scoring system.

Item scores for items 9 to 37 are abbreviated with I9 to I37.

To calculate the (raw) HRQoL total score, the values of the individual subscales are summed (note that this is not the sum of the individual items). Transformed HRQoL total scores based on the formula above can be obtained as well.

For the subscale analyses, if < 50% of items of a subscale is missing, the subscale should be retained with the mean subscale score generated based on the non-missing items ("half item rule"). If \geq 50% of the items are missing, no subscale score should be calculated, and the subscale score should be considered missing. If one or more subscale scores are missing, the HRQoL total score is not calculated.

Appendix 5: List of laboratory parameters

Table 9–5: List of laboratory parameters

to useLaboratory categoryLaboratory testSmallVITAMINS25-Hydroxyvitamin DCOAGULATIONActivated Partial Thromboplastin TimeHORMONESAdrenocorticotropic HormoneGENERAL CHEMISTRYAlanine AminotransferaseGENERAL CHEMISTRYAlbuminGENERAL CHEMISTRYAlbuminGENERAL CHEMISTRYAlkaline PhosphataseIMMUNOLOGYAlpha-1 AntitrypsinIMMUNOLOGYAnti Mitochondiral AntibodyIMMUNOLOGYGENERAL CHEMISTRYIMMUNOLOGYAntinuclear AntibodiesGENERAL CHEMISTRYHEMATOLOGY	lest Largest X X X X X X X X X X X X X X X X X
VITAMINS25-Hydroxyvitamin DCOAGULATIONActivated Partial Thromboplastin TimeHORMONESAdrenocorticotropic HormoneGENERAL CHEMISTRYAlanine AminotransferaseGENERAL CHEMISTRYAlbuminGENERAL CHEMISTRYAlkaline PhosphataseIMMUNOLOGYAlpha-1 AntitrypsinIMMUNOLOGYAnti Mitochondiral AntibodyIMMUNOLOGYAntinuclear AntibodiesGENERAL CHEMISTRYAspartate Aminotransferase	X X X X X X X X X X X X X X X X
COAGULATIONActivated Partial Thromboplastin TimeHORMONESAdrenocorticotropic HormoneGENERAL CHEMISTRYAlanine AminotransferaseGENERAL CHEMISTRYAlbuminGENERAL CHEMISTRYAlkaline PhosphataseIMMUNOLOGYAlpha-1 AntitrypsinIMMUNOLOGYAnti Mitochondiral AntibodyIMMUNOLOGYAntinuclear AntibodiesGENERAL CHEMISTRYAspartate Aminotransferase	X X X X X X X X X X X X X X X X X X X
HORMONESAdrenocorticotropic HormoneGENERAL CHEMISTRYAlanine AminotransferaseGENERAL CHEMISTRYAlbuminGENERAL CHEMISTRYAlkaline PhosphataseIMMUNOLOGYAlpha-1 AntitrypsinIMMUNOLOGYAnti Mitochondiral AntibodyIMMUNOLOGYAntinuclear AntibodiesGENERAL CHEMISTRYAspartate Aminotransferase	X X X X X X X X X X X X X X X X X X X
GENERAL CHEMISTRYAlanine AminotransferaseGENERAL CHEMISTRYAlbuminGENERAL CHEMISTRYAlkaline PhosphataseIMMUNOLOGYAlpha-1 AntitrypsinIMMUNOLOGYAnti Mitochondiral AntibodyIMMUNOLOGYAntinuclear AntibodiesGENERAL CHEMISTRYAspartate Aminotransferase	X X X X X X X
GENERAL CHEMISTRYAlbuminGENERAL CHEMISTRYAlkaline PhosphataseIMMUNOLOGYAlpha-1 AntitrypsinIMMUNOLOGYAnti Mitochondiral AntibodyIMMUNOLOGYAntinuclear AntibodiesGENERAL CHEMISTRYAspartate Aminotransferase	X X X X X X X X X X X X
GENERAL CHEMISTRYAlkaline PhosphataseIMMUNOLOGYAlpha-1 AntitrypsinIMMUNOLOGYAnti Mitochondiral AntibodyIMMUNOLOGYAntinuclear AntibodiesGENERAL CHEMISTRYAspartate Aminotransferase	X X X X X X
IMMUNOLOGYAlpha-1 AntirypsinIMMUNOLOGYAnti Mitochondiral AntibodyIMMUNOLOGYAntinuclear AntibodiesGENERAL CHEMISTRYAspartate Aminotransferase	X X X X X
IMMUNOLOGYAnti Mitochondiral AntibodyIMMUNOLOGYAntinuclear AntibodiesGENERAL CHEMISTRYAspartate Aminotransferase	x x x x x
IMMUNOLOGYAntinuclear AntibodiesGENERAL CHEMISTRYAspartate Aminotransferase	x x x x
GENERAL CHEMISTRY Aspartate Aminotransferase	x x x x
	X X
HEMATOLOGY Basophils	
HEMATOLOGY Basophils/Leukocytes	Х
GENERAL CHEMISTRY Bilirubin	Х
URINALYSIS Bilirubin	Х
URINALYSIS Blood	х
GENERAL CHEMISTRY Bone Specific Alkaline Phosphatase	х
MICROBIOLOGY Brucellae	Х
GENERAL CHEMISTRY Calcium	х х
PROTEINS Ceruloplasmin	х
GENERAL CHEMISTRY Chloride	х
GENERAL CHEMISTRY Cholesterol	х
Choriogonadotropin Beta	х
HORMONES Choriogonadotropin Beta	X
URINALYSIS Choriogonadotropin Beta	X
HORMONES Cortisol	X X
GENERAL CHEMISTRY Creatine Kinase	XXX
GENERAL CHEMISTRY Creatinine	X
IMMUNOLOGY Cytomegalovirus DNA	X
, 3	x
HEMATOLOGY Eosinophils	X
HEMATOLOGY Eosinophils/Leukocytes	X
IMMUNOLOGY Epstein-Barr Capsid IgG Antibody	X
IMMUNOLOGY Epstein-Barr Capsid IgM Antibody	X
IMMUNOLOGY Epstein-Barr Nuclear Antigen 1 IgG Ab	Х
HEMATOLOGY Ery. Mean Corpuscular Hemoglobin	Х
HEMATOLOGY Ery. Mean Corpuscular Volume	Х
HEMATOLOGY Erythrocytes	Х
HORMONES Estradiol	х
GENERAL CHEMISTRY Ferritin	Х
HORMONES Follicle Stimulating Hormone	х
GENERAL CHEMISTRY Gamma Glutamyl Transferase	х
URINALYSIS Glucose	х
IMMUNOLOGY HCV PCR Viral Load	Х
GENERAL CHEMISTRY HDL Cholesterol	x x
HEMATOLOGY Hematocrit	х
HEMATOLOGY Hemoglobin	х
GENERAL CHEMISTRY Hemoglobin A1C	х
IMMUNOLOGY Hepatitis A Virus Antibody	х
IMMUNOLOGY Hepatitis A Virus Antibody IgM	х
IMMUNOLOGY Hepatitis B Virus Core Antibody	X
IMMUNOLOGY Hepatitis B Virus DNA	X
IMMUNOLOGY Hepatitis B Virus Surface Antibody	x
IMMUNOLOGY Hepatitis B Virus Surface Antibody	x
IMMUNOLOGY Hepatitis B Virus Surface Antigen	X
IMMUNOLOGY Hepatitis D Virus Antibody	X
IMMUNOLOGY Hepatitis D Virus IgG Antibody	X
IMMUNOLOGY Hepatitis D Virus IgM Antibody	X
IMMUNOLOGY Hepatitis D Virus RNA	Х
IMMUNOLOGY Hepatitis E Virus Antibody	Х
IMMUNOLOGY Hepatitis E Virus IgG Antibody	Х

Page: 58 of 58

Table 9–5: List of laboratory parameters

			In case of multiple measurements	
		for a patient, which measur		
		to use		
Laboratory category	Laboratory test	Smallest	Largest	
IMMUNOLOGY	Hepatitis E Virus IgM Antibody		Х	
IMMUNOLOGY	Hepatitis E Virus RNA		Х	
IMMUNOLOGY	Herpes Simplex Virus 1 IgG Antibody		Х	
IMMUNOLOGY	Herpes Simplex Virus 1 IgM Antibody		Х	
IMMUNOLOGY	Immunoglobulin A		Х	
IMMUNOLOGY	Immunoglobulin G		Х	
IMMUNOLOGY	Immunoglobulin M		Х	
GENERAL CHEMISTRY	Iron	Х		
URINALYSIS	Ketones		Х	
GENERAL CHEMISTRY	Lactate Dehydrogenase		Х	
GENERAL CHEMISTRY	LDL Cholesterol		Х	
MICROBIOLOGY	Leptospirae		Х	
HEMATOLOGY	Leukocytes	Х		
URINALYSIS	Leukocytes		Х	
HORMONES	Luteinizing Hormone		Х	
HEMATOLOGY	Lymphocytes	Х		
HEMATOLOGY	Lymphocytes/Leukocytes		х	
HEMATOLOGY	Monocytes	Х		
HEMATOLOGY	Monocytes/Leukocytes		х	
IMMUNOLOGY	MPO ANCA		х	
HEMATOLOGY	Neutrophils	х		
HEMATOLOGY	Neutrophils/Leukocytes		х	
URINALYSIS	Nitrite		х	
GENERAL CHEMISTRY	Osteocalcin		X	
HEMATOLOGY	Platelets	Х	~	
GENERAL CHEMISTRY	Potassium	X	х	
IMMUNOLOGY	PR3 ANCA	^A	X	
HORMONES	Progesterone	х	A	
HORMONES	Prolactin	K	х	
GENERAL CHEMISTRY	Protein		x	
URINALYSIS	Protein		X	
COAGULATION	Prothrombin Intl. Normalized Ratio	х	~	
COAGULATION	Prothrombin Time	X	х	
GENERAL CHEMISTRY	Pseudocholinesterase		x	
IMMUNOLOGY			×	
	Smooth Muscle Antibody Sodium	х	^	
GENERAL CHEMISTRY		Α	v	
HORMONES	Testosterone	V	x	
	Thyrotropin	Х	x	
GENERAL CHEMISTRY	Time to event		x	
GENERAL CHEMISTRY	Total Iron Binding Capacity		x	
	Toxoplasma gondii antibody		x	
GENERAL CHEMISTRY	Triglycerides		Х	
GENERAL CHEMISTRY	Type I Collagen C-Telopeptides		x	
URINALYSIS	Urobilinogen		Х	
	all parameters not otherwise specified		Х

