## 6.2 Exclusion criteria

*This section was changed in Amendment 1, see Section 15.1.1*

1. Pregnancy or lactation (less than 3 months since delivery, abortion, or lactation before start of treatment)
2. Hypersensitivity to any ingredient of the study drug
3. Hemoglobin values  $\leq 6$  g/dL or any condition requiring immediate blood transfusion (subjects with hemoglobin values  $\leq 10.9$  g/dL will be recommended to use iron supplementation).
4. Any diseases, conditions, or medications that can compromise the function of the body systems and could result in altered absorption, excessive accumulation, impaired metabolism, or altered excretion of the study drug including, but not limited to:
  - Impaired function of the kidneys (laboratory values outside of inclusion range)
  - Abnormal liver parameters (presence of at least one of the following criteria, please see also section 9.6.3.1 Laboratory evaluations):
    - 2 x upper limit of normal (ULN) for glutamic oxaloacetic transaminase (GOT) / aspartate aminotransferase (AST)
    - 2 x ULN for glutamic pyruvic transaminase (GPT) / alanine aminotransferase (ALT)
    - 2 x ULN for alkaline phosphatase (AP)
    - Total bilirubin outside the upper limit of normal range
    - International normalized ratio (INR) outside the upper limit of the normal
  - Diagnosis of hepatitis B infection, i.e., Hbs-antigen positive at Visit 1
  - Diagnosis of hepatitis C infection, i.e., hepatitis C-antibodies and HCV-RNA positive at Visit 1
  - Chronic bowel diseases, eg, M. Crohn and Colitis ulcerosa

---

 As specified in the laboratory manual and in the reports from the central laboratory

 For the liver-related laboratory parameters ALT, AST, and AP the laboratory test also needs to be repeated if results of the first test at visit 1 are raised above the ULN, but still  $< 2x$  ULN (i.e. still within inclusion range). The patient is eligible only if the second test shows a stabilization or decline in those values (see Section 9.6.3.1).

 As specified in the laboratory manual and in the reports from the central laboratory.

 As specified in the laboratory manual and in the reports from the central laboratory.

 This will be applied only to subjects newly enrolled into the study after protocol version 3.0 has become valid

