#### **Hemoglobin (Hb concentration)**

**Serum chemistry:** creatinine, chloride, potassium, sodium, calcium, total protein, albumin, total cholesterol, high density lipoprotein (HDL) cholesterol, low density lipoprotein (LDL) cholesterol, triglycerides, ALT, AST, AP, gamma-glutamyl transpeptidase ( $\gamma$  GT), and total bilirubin (in case the result is  $> 2xULN$ , conjugated and unconjugated bilirubin will be determined).

See Section [9.6.1.6](#) for procedure in case of elevated liver parameters.

**Biochemistry:** glycosylated hemoglobin (HbA1c) and ferritin.

**Additional parameters:** hormones (follicle-stimulating hormone [FSH], luteinizing hormone [LH], estradiol [E2], progesterone [P], prolactin, thyroid-stimulating hormone [TSH]), and vitamin D (serum 25-hydroxyvitamin D).

**In case of elevated liver enzymes requiring investigation of alternative cause the following parameters will have to be determined (in earlier CSP versions this was summarized in a particular section “close observation”):**

Serum chemistry panel (see above), A1AT level, conjugated bilirubin, ceruloplasmin, cholinesterase, CK, ferritin, full blood count (incl. eosinophilia), hemoglobin, INR, iron, LDH, platelets, PT, total iron binding capacity (TIBC), testing to rule out Hepatitis A-, Hepatitis B-, Hepatitis C, Hepatitis E-, Cytomegalie-, Epstein-Barr-, and Herpes simplex virus infection, brucellosis, leptospirosis, and toxoplasmosis. ANA/ANCA screening with further tests depending on result and IgA, IgG, and IgM, potentially also testing to out Hepatitis D.

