6.4.2.3 Laboratory parameters

Laboratory parameters which will be descriptively analyzed are included in Appendix 5. The tabulation of laboratory data will follow in principle the Bayer Global Standard Tables catalogue (currently version 4.0 default), with the necessary modifications like for time interval presentation instead of visit presentation. Treatment-emergent high and low laboratory abnormalities will be summarized by treatment periods (TP1, TP2) and overall.

For immunology and coagulation parameters Intervals 'BL/Post baseline' will be used, while for all other parameters Intervals C will be used (see Figure 4–1). If several laboratory measurements are available for a patient, depending on the laboratory parameter only either the smallest (if small values are considered worse for the parameter) or largest (if large values are considered worse) measurement within Intervals C will be used (see Appendix 5 for details). If both largest and smallest values are specified for a particular parameter, two separate analyses will be done for this parameter, one analysis using the patient's largest measurement across the considered time period and another analysis using the smallest measurement. Both scheduled and unscheduled measurements will be considered.

Central as well as local lab measurements are available. Descriptive statistics will be provided for central lab measurements. Local lab measurements will be listed.

Values below the lower limit of quantification (LLOQ) will be set to LLOQ/2. Values above the upper limit of quantification (ULOQ) will be set to ULOQ.

Estradiol

Absolute values will be analyzed using descriptive statistics by treatment group using Interval C and Interval D (see Figure 4–1). The smallest value (i.e. "worst case") per patient per time interval will be used in the analyses.

The distribution of estradiol values by treatment group using Intervals C and D will be graphically depicted with boxplots. The time course will be shown using line plots depicting the mean and 95% confidence interval (two-sided) and using Intervals C and D as described above. Time intervals including data from less than 10 patients in the respective group will be excluded from the plots.

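### SAP Table 9-5 appears to select the smallest INR as a woman's worst value, although only a high INR is a concern in the protocol

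*SAP*

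**What the plan says.** SAP 6.4.2.3 states that, when a patient has several measurements, the analysis uses "only either the smallest (if small values are considered worse for the parameter) or largest (if large values are considered worse) measurement", and refers to Appendix 5 for the direction of each parameter. It also allows a two-sided option: "If both largest and smallest values are specified for a particular parameter, two separate analyses will be done for this parameter".

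Table 9-5 in Appendix 5 has two mark columns, Smallest and then Largest, under a header that begins "In case of multiple measurements". The row "Prothrombin Intl. Normalized Ratio" carries its mark in the first of these columns. The last row of the table sends every parameter not otherwise listed to Largest.

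On time intervals, SAP 6.4.2.3 says: "For immunology and coagulation parameters Intervals 'BL/Post baseline' will be used".

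The protocol refers to INR in these places:
- Section 6.2 excludes women with "International normalized ratio (INR) outside the upper limit of the normal".
- Section 6.4.1 includes INR above 1.5, in combination with ALT or AST above 3 x ULN, among the criteria for withdrawal from study treatment.
- Section 9.6.3.1 lists INR among the tests for "elevated liver enzymes requiring investigation of alternative cause".
- Section 9.6.3.9 names it as an example of additional liver function tests to obtain as appropriate.

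**The concern.** The table's direction for INR contradicts the rule it is meant to implement. A worst-value rule is there so that a transient abnormality survives the reduction to one value per woman. Pointed the wrong way, it keeps the most reassuring value.

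This matters more for INR than for a routine parameter. The laboratory panels for the safety closeout visit in protocol 9.6.3.1 do not list INR. The current text asks for it in the work-up of raised liver enzymes. The women with INR values after baseline are therefore likely to include those of hepatic interest. SAP 6.4.2.8 builds its liver tables, plots and listings from AST, ALT, AP and bilirubin, so the standard coagulation summary is the only planned descriptive summary of INR values.

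**Working it through.** The plan gives no figure to reproduce. The check has three parts: which column is marked, which direction is worse, and what the selection does to a series of values.

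**1. Which column is marked.** In the extracted text the INR row reads as a mark under Smallest followed by a tilde under Largest. The tilde is most likely noise:
- Platelets, where a low value is plainly the worse one, shows the same mark and tilde.
- Progesterone and Sodium have other stray characters (a letter A and a caret) in the same position.
- Potassium reads as a clear mark in both columns, so a genuine two-sided entry can survive extraction.
- Rows marked only under Largest, such as Pseudocholinesterase and Triglycerides, have an empty Smallest cell.

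Smallest only is therefore the best reading, but it is not certain. The next row, Prothrombin Time, reads as marked in both columns. Because stray characters also occur in Smallest cells nearby (Prolactin, Testosterone), that row needs the same check.

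**2. Which direction is worse.**

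| Source | Direction of concern for INR |
|---|---|
| Protocol 6.2, exclusion | Above the upper limit of normal |
| Protocol 6.4.1, treatment withdrawal | Above 1.5, with ALT/AST above 3 x ULN |
| SAP 6.4.2.3, general rule | Use the largest if large values are worse |
| SAP Table 9-5, INR row | Smallest |

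Nothing in either document treats a low INR as a concern. The first three rows agree with each other and the fourth does not.

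**3. Effect of the selection.** The summary value is min(x) under Smallest and max(x) under Largest, taken over the single post-baseline interval. The series below are assumed, for illustration only.

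| Assumed post-baseline INR values | Smallest | Above 1.5? | Largest | Above 1.5? |
|---|---|---|---|---|
| 1.8 | 1.8 | yes | 1.8 | yes |
| 1.0, 1.8 | 1.0 | no | 1.8 | yes |
| 1.0, 1.6, 1.8, 1.2, 1.0 | 1.0 | no | 1.8 | yes |
| 1.6, 2.1, 1.7 | 1.6 | yes | 2.1 | yes |

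There are three cases:
- One value: the two rules agree.
- Several values, at least one of them normal: Smallest misses the rise.
- Several values, all raised but differing: Smallest understates the rise. In the last row the shortfall is 2.1 - 1.6 = 0.5.

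The post-baseline interval is not subdivided for coagulation, so one normal value at any time after the start of treatment is enough to replace the peak.

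**The case against.** **The cell may be misread.** If the tilde is a damaged X, INR is analysed both ways under SAP 6.4.2.3 and the point falls. This stands as a condition: the neighbouring rows make noise the better explanation, but only the original PDF can settle it.

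**The rule is worded for other intervals.** The sentence in SAP 6.4.2.3 reads "largest (if large values are considered worse) measurement within Intervals C will be used", while coagulation is assigned to the BL/Post baseline split. Read literally, the SAP does not say which value to take for INR. The header of Table 9-5 is general and the table lists coagulation tests, so applying the rule to INR is the natural reading. The gap is real, however, and needs closing in any case.

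**A rise can be seen elsewhere.** This also stands. A reader might infer that a liver event with a raised INR would vanish from the report. The documents do not support that:
- Protocol 9.6.1.1 requires liver tests that meet the withdrawal criteria to be reported as SAEs.
- Protocol 9.6.1.6 makes liver cases that qualify for close observation or for investigation of cause AESIs.
- SAP 6.4.2.4.2 summarises SAEs, and both tabulates and lists AESIs.
- SAP 6.4.2.3 summarises treatment-emergent high and low abnormalities.
- SAP 4.1 and 4.5 provide data listings.

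Nor is the coagulation summary described anywhere as the display intended to show INR in liver events.

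**The number affected is unknown.** A reader might also infer that INR is measured repeatedly in most liver cases, or that every woman with two values is affected. Neither has a source. Protocol 9.6.3.9 asks for a repeat of the serum chemistry panel, which does not include INR, and leaves INR to judgement. The values must also differ, and must come from the central laboratory, because SAP 6.4.2.3 only lists local results.

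**Conclusion.** The point holds in a limited form. On the best reading of Table 9-5, INR is selected in the wrong direction under the SAP's own rule. For a woman with two or more differing central-laboratory values after baseline, the descriptive coagulation summary would understate a rise or miss it.

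The conclusion rests on two assumptions: that the INR mark is under Smallest only, and that the selection rule extends to the BL/Post baseline intervals. The number of women affected cannot be derived from the documents and may be small.

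No hypothesis test or efficacy result depends on this, and it does not make liver events invisible. It is a correction to one safety summary, worth making because that is the only descriptive summary planned for INR values.

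**What to change.** 1. Check the INR and Prothrombin Time marks in the original PDF of Table 9-5. If INR is in fact marked under both columns, only step 3 remains for INR.
2. Otherwise mark INR under Largest, or under both columns if a two-sided summary is wanted. Correct Prothrombin Time if its mark under Smallest turns out to be unintended.
3. Add a clause to SAP 6.4.2.3 stating that the smallest/largest selection in Appendix 5 also applies to the BL/Post baseline intervals used for coagulation. SAP 4.5 uses the worst measurement for baseline in interval-based analyses, so the same direction should apply before and after the start of treatment.

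The cost is one table cell (two if Prothrombin Time also needs correcting), one clause and one programming flag. No additional data are needed, and the efficacy analyses and alpha are untouched.
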